#### Nonclinical Assessment of Safety

Extensive nonclinical safety core battery studies have been conducted in the rat and the Beagle dog to evaluate the effects of apramycin on organ systems (IB 2021).

Repeat-dose toxicity studies identified the kidneys as the main target organ of toxicity. Nephrotoxicity manifested as increases in plasma creatinine and BUN, and histopathological changes in the kidney, primarily tubular necrosis with or without regeneration. Nephrotoxicity was exposure-related, with a lower incidence and severity after the recovery period, suggesting potential reversibility. Nephrotoxicity appeared to correlate better with cumulative exposure than with total AUC (0-24) (IB 2021).

Ototoxicity is a known risk of aminoglycosides. A repeat, 16-day dose study in guinea pigs showed that apramycin ototoxicity progressed more gradually than under gentamicin treatment, and cochlear function was partly retained even at high concentrations (430 mg apramycin/kg body weight). "No ototoxic effects were observed in the guinea pig model at the 152 mg/kg/day dose level. This would convert to a human equivalent dose (HED) of 33.3 mg/kg, a single dose exposure of 0.8 mMÅ~h, and a cumulated exposure of 13.7 mMÅ~h, all of which are markedly higher than the nephrotoxic no observed adverse effect levels (NOAELs) in both rats and dogs." (Matt 2012) Recent literature data support the finding that apramycin is of lower ototoxicity than gentamicin (Ishikawa 2019).

Besides nephrotoxicity and ototoxicity, no other noteworthy findings in clinical signs and symptoms were observed. Apramycin showed no effects on the CNS, cardiovascular, or respiratory systems (IB 2021).

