## 5.1 Subject Inclusion Criteria

All must be answered YES for the subject to be eligible for study participation:

- 1. Subject reads and signs the Informed Consent Form (ICF) and agree to have bronchoscopy with bronchoalveolar lavage under sedation or light anesthesia and comply with study procedures.
- 2. Healthy male or non-pregnant, non-lactating female subjects 18 to 45 years of age (both inclusive) at the time of dosing.
  - a. Note 1: Determined by medical history (MH), medication use, physical examination (PE), and vital signs, clinical laboratory tests and 12-lead ECG within reference ranges at Screening and Day-2. (See Sections 8.1 and 8.2, Appendix B, Table 2, Table 3 and Table 4 and the study-specific MOP.)

Exceptions to BP, HR and laboratory test values being with normal ranges are:

- Abnormal HR and BP on first measurement may be repeated twice more with the subject resting between measurements for at least 5 min according to Section 8.1.6.
- Subjects with baseline  $HR \ge 45$  to 50 bpm may be accepted if otherwise healthy adults with known history of asymptomatic bradycardia.
- Subjects with baseline SBP up to 140 mmHg and DBP up to 90 mmHg may be accepted if otherwise healthy.
- A laboratory value that is Grade 1 will be allowed if not considered to be clinically significant by the investigator, with the exception of ALT, AST, AP, BUN, urine protein, serum creatinine or estimated glomerular filtration rate (eGFR) <70 mL/min /1.73 m^2 by the Chronic Kidney Disease Epidemiology collaboration (CKD-EPI) equation.
- 3. Female subjects of childbearing potential should use highly effective methods of contraception from the time of screening to 30 days after dosing.
  - Note 1: A female is considered of childbearing potential unless post-menopausal (defined as history of ≥1 year of spontaneous amenorrhea and a FSH level >40 IU/L), or permanently surgically sterilized.

- Note 2: Highly effective contraceptive methods include: (a) surgical sterilization methods, such as tubal ligation, bilateral oophorectomy, salpingectomy, hysterectomy, or successful tubal obliteration (e.g., Essure®) with documented radiological confirmation test at least 90 days after the procedure, or (b) long-acting reversible contraception, such as progestin-releasing subdermal implants, copper intrauterine devices (IUDs), levonorgestrel-releasing IUDs.

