### 9.5 Halting Rules

#### 9.5.1 Study Halting Criteria

Systemic or Lab Criteria:

- One subject has an SAE that is determined to be related to the study product. OR
- Two or more subjects experience Grade 2 or higher related TEAE (laboratory or systemic) that is coded in the same HLGT per MedDRA classification, and if AE is not resolved within 48 hours through Day 4. Resolution is defined as return to a baseline status. Note: If the event starts on Day 4, the review period will be extended to Day 5.

Note: VS abnormalities will be considered part of a systemic disorder or an organspecific condition, as described in Appendix B: Adverse Events Toxicity Grading Criteria, in order to be included among the Study Halting Criteria.

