#### Secondary:

- Type and incidence of treatment-emergent adverse events (TEAEs) and serious AEs (SAEs) to Day 30 (± 4 days) after dosing.
- Frequency of clinically significant TEAEs in physical examination (PE) findings and of changes from baseline in vital signs and clinical laboratory parameters until Day 14 (± 3 days) after dosing.
- Frequency of changes in electrocardiogram (ECG) intervals (QTcF, PR, QRS, heart rate [HR]), and of morphological changes from baseline until 24 ± 1 h after dosing.

• Type and incidence of TEAEs related to auditory (cochlear) function tests (pure-tone audiometry and distortion product otoacoustic emissions [DPOAEs]) to Day 30 (± 4 days) after dosing.

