- The proportion of participants with abnormal laboratory results by parameter and timepoint will be summarized for CHEM (Table 27 for the Safety Population and Table 28 for the Safety Subset Population), HEM (Table 33 for the Safety Population and Table 34 for the Safety Subset Population), COAG (Table 39 for the Safety Population and Table 40 for the Safety Subset Population), and UA (Table 45 for the Safety Population and Table 46 for the Safety Subset Population).
- The proportion of participants with mild, moderate, or severe laboratory results by parameter and timepoint will be summarized for CHEM (Table 29 for the Safety Population and Table 30 for the Safety Subset Population), HEM (Table 35 for the Safety Population and Table 36 for the Safety Subset Population), COAG (Table 41 for the Safety Population and Table 42 for the Safety Subset Population), and UA (Table 47 for the Safety Population and Table 48 for the Safety Subset Population).
- Summary statistics of measurements and change from baseline by parameter and timepoint for CHEM (Table 31 for the Safety Subset Population and Table 32 for the Safety Population), HEM (Table 37 for the Safety Population and Table 38 for the Safety Subset Population), and COAG (Table 43 for the Safety Population and Table 44 for the Safety Subset Population). UA character results will be excluded from change from baseline summaries.
- Change from baseline at each scheduled timepoint will be visualized using box plots for each parameter. The safety population used for each figure will be noted in the title. UA character results will be excluded from graphical summaries.
  - CHEM: Beginning at Figure 7 and continuing through Figure 46
  - HEM: Beginning at Figure 47 and continuing through Figure 64

#### • COAG: Figure 65, Figure 66, Figure 67, Figure 68, Figure 69, and Figure 70

Screening laboratory results will be listed. Serology result will be shown in Listing 14. Urine drug and cotinine and alcohol breathalyzer test results will be shown in Listing 15. Pregnancy testing and FSH test results will be shown in Listing 16.

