#### 12.4.1 Individual Laboratory Measurements and Abnormal Laboratory Values

#### Table 4: Clinical Laboratory Reference Ranges and Toxicity Grading Scales

Laboratory AEs	Reference Ranges	Mild (Grade 1)	Moderate (Grade 2)	Severe (Grade 3)
Blood, serum, or plasma	Ranges	(Grade I)	(Grade 2)	(Grade b)
HEMATOLOGY				
Hemoglobin decrease, female – g/dL	11.1 – 15.9	9.6 - 11.0	8.0 - 9.5	<8.0
Hemoglobin decrease. male – g/dL	13.0 - 17.7	11.0 - 12.9	8.5 - 10.9	<8.5
WBC increase $- x10^3 / \mu L$	3.4 - 10.8	>10.8 - 15.0	>15.0 - 20.0	>20.0
WBC decrease $-x10^3/\mu L$	3.4 - 10.8	2.4 - <3.4	1.4 - <2.4	<1.4
Neutrophils decrease $- x 10^{3/} \mu L$	1.4 - 7.0	1.0-<1.4	0.75 - <1.0	< 0.75
Lymphocytes decrease $-x10^3/\mu L$	0.7 - 3.1	<0.7 -0.4	<0.4 - 0.3	<0.30
Monocytes increase $-x10^3/\mu L$	0.1 - 0.9	>0.9 - 2.0	>2.0 - 3.0	>3.0
Eosinophils increase $- x 10^3 / \mu L$	0.0 - 0.4	>0.4 - 0.75	>0.75 - 1.0	>1.0
Basophils increase $- x10^{3}/\mu L$	0.0-0.2	>0.2 - 0.5	>0.5-0.8	>0.8
Platelets decrease $- x 10^3 / \mu L$	150 - 450	90 - <150	55 - <90	<55
COAGULATION				
PT INR	0.9 - 1.2	>1.2-1.8	>1.8-2.1	>2.1
Prothrombin Time	9.1 - 12.0	>12.0-15.0	>15.0-18.6	>18.6
Activated Partial Thromboplastin Time (APTT)	24 - 33	>33.0-54.0	>54.0-75.0	>75.0
CHEMISTRY		I		
Sodium decrease – mmol/L	134 - 144	130 - 133	124 –129	<124
Sodium increase – mmol/L	134 - 144	145 - 150	151 – 156	>156
Potassium increase – mmol/L	3.5 - 5.2	5.3 - 6.0	6.1 - 6.5	>6.5
Potassium decrease – mmol/L	3.5 - 5.2	3.4-3.2	2.5 - 2.9	<2.5
Total Carbon Dioxide (CO 2 ) increase – mmol/L	20 - 29	30 - 35	36 - 37	>37
Total Carbon Dioxide (CO2) decrease – mmol/L	20-29	17 - 19	14 - 16	<14
Calcium decrease – mg/dL	8.7 - 10.2	7.8 - 8.6	7.0 - 7.7	<7.0
Calcium increase – mg/dL	8.7 - 10.2	10.3 - 11.4	11.5 - 12.5	>12.5
Magnesium decrease – mg/dL	1.6 - 2.3	1.2 - 1.5	1.1 - 0.9	<0.9
Blood urea nitrogen (BUN) increase, 18-39Y - mg/dL	6-20	21 - 58	59-120	>120
Blood urea nitrogen (BUN) increase, 40-59Y – mg/dL	6-24	25 - 58	59 - 120	>120
Glucose decrease, fasting – mg/dL	65 – 99	47 - 64	42 - 46	<42
Glucose increase, fasting – mg/dL	65 – 99	100 - 160	161 - 250	>250
Creatinine increase, male – mg/dL	0.76 - 1.27	1.28 - 1.90	1.91 - 3.80	>3.80
Creatinine increase, female – mg/dL	0.57 - 1.00	0.58 - 1.50	1.51 - 3.00	>3.00
Direct bilirubin	0.0 - 0.40	0.41 - 0.70	0.71 - 1.20	>1.20
Total bilirubin (serum) increase – mg/dL (with other LFTs in the normal range)	0.0 - 1.2	1.3 - 2.0	2.1 - 2.5	>2.5

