#### **12.4.1** Individual Laboratory Measurements and Abnormal Laboratory Values

#### Table 4: Clinical Laboratory Reference Ranges and Toxicity Grading Scales (Continued)

Laboratory AEs	Reference Ranges	Mild (Grade 1)	Moderate (Grade 2)	Severe (Grade 3)			
Albumin decrease, Female, 18-30Y - g/dL	3.9 - 5.0	3.8 - 3.5	2.0-2.9	<2.0			
Albumin decrease, Male, 31-50Y – g/dL	4.0 - 5.0	3.9 - 3.5	2.0-2.9	<2.0			
Albumin decrease, Female, 31-50Y – g/dL	3.8 - 4.8	3.7 – 3.5	2.0-2.9	<2.0			
AST increase – U/L	0-40	41 - 80	81 - 120	>120			
ALT increase, male – U/L	0-44	45-88	89 - 132	>132			
ALT increase, female – U/L	0 - 32	33 - 64	65 - 96	>96			
Alkaline phosphatase (AP) increase, males 18-20Y - U/L	51 - 125	126 - 250	251 - 375	>375			
Alkaline phosphatase (AP) increase, females, 18-20Y - U/L	42 - 106	107 - 250	251 - 375	>375			
Alkaline phosphatase (AP) increase, 21-150Y – U/L	44 - 121	122 - 250	251 - 375	>375			
Urine							
URINALYSIS by Dipstick							
Protein	negative / trace	1+	2+	>2+			
Blood (occult)	negative	1+	2+	>2+			
Glucose	negative	1+	2+	>2+			
URINE MICROSCOPY							
Red blood cells (RBC) per HPF	0 - 2	6-10	11-50	>50 and/or gross blood			
WBC (microscopic) – WBC per HPF	0 - 5	6-10	11-50	>50			
Bacteria (microscopic)	none / few	few	moderate	many			
Note 1: With the exception of AST ALT AP bilightin electrolytes urine protein BUN and creatining which should be within reference							

Note 1: With the exception of AST, ALT, AP, bilirubin, electrolytes, urine protein, BUN and creatinine, which should be within reference range, lab values of other analytes in the grade 1 range are acceptable for enrollment if (a) they are not considered to be clinically significant by the investigator and (b) there is no cluster of abnormal labs that combined are suggestive of an underlying disorder.

Note 2: Other Exceptions to screening laboratory tests' normal reference ranges are:

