### Table 64: ECG Change from Time-Matched Baseline by Parameter and Timepoint – Safety Subset Population

			ategory							
		QTcF >450 - 480 msec	QTcF >480 - 500 msec	QTcF >500 msec	QTcF increase ≥30 – 59 msec from baseline	QTcF increase ≥60 msec from baseline				
Timepoint	Ν	n (%)	n (%)	n (%)	n (%)	n (%)				
Day 1, 1 h Post-Dose	х	x (xx)	x (xx)	x (xx)	x (xx)	x (xx)				
Day 1, 4 h Post-Dose	x	x (xx)	x (xx)	x (xx)	x (xx)	x (xx)				
Day 1, 16 h Post-Dose	х	x (xx)	x (xx)	x (xx)	x (xx)	x (xx)				
Day 2, 24 h Post-Dose	x	x (xx)	x (xx)	x (xx)	x (xx)	x (xx)				
Day 2, 36 h Post-Dose	х	x (xx)	x (xx)	x (xx)	x (xx)	x (xx)				
Day 3, 48 h Post-Dose	х	x (xx)	x (xx)	x (xx)	x (xx)	x (xx)				
Day 3, 60 h Post-Dose	х	x (xx)	x (xx)	x (xx)	x (xx)	x (xx)				
Day 14	х	x (xx)	x (xx)	x (xx)	x (xx)	x (xx)				
Notes: $N = Number of participants in the Safety Population with the ECG measurement assessed at the respective timepoint. n = Number of participants who experienced the event. A participant may be counted in more than one category. Pre-Dose Baseline = The most recent measurement prior to start of infusion.$										

 Table 65:
 Categorical Summary of QTcF Interval by Timepoint – Safety Population

Table with similar format:

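### No planned table counts participants by change in creatinine or eGFR from their own baseline, although the secondary endpoint is worded as a frequency of such changes

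*SAP*

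**What the plan says.** - **Endpoint.** SAP 3.2 lists as a secondary endpoint the frequency "of changes from baseline in vital signs and clinical laboratory parameters" up to Day 14. Protocol 3.2.2 has the same endpoint.
- **Target organ.** Protocol 2.2, Nonclinical Assessment of Safety: "Repeat-dose toxicity studies identified the kidneys as the main target organ of toxicity".
- **Counts.** SAP 9.6: "The proportion of participants with mild, moderate, or severe laboratory results by parameter and timepoint will be summarized for CHEM" (Tables 29 and 30). Tables 27 and 28 count results that are abnormally low or high.
- **Limits.** SAP Table 4 sets fixed values, as in the row "Creatinine increase, male – mg/dL". It has no row for eGFR.
- **Change from baseline.** Tables 31 and 32 give mean, SD, median, minimum and maximum change. Figures 15 to 18 are box plots for creatinine and eGFR, and Listing 9 shows each participant's change. Cystatin C and KIM-1 changes are in Tables 49 and 50 and Figures 71 to 76.
- **ECG.** Table 65 counts participants above absolute QTcF limits and also by rise, with columns such as "QTcF increase ≥60 msec from baseline". Table 67 counts percentage changes in PR, QRS and heart rate.
- **Entry.** Note 1 to SAP Table 4 withholds the Grade 1 allowance from several analytes, among them "electrolytes, urine protein, BUN and creatinine, which should be within reference" range. Protocol 5.1, criterion 2, makes a similar exception for creatinine and for eGFR below 70 mL/min/1.73 m².

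**The concern.** A frequency of change needs a count of participants whose value has moved by some amount from where it started. For creatinine the planned counts depend only on where the value ends relative to a fixed limit. Participants enter with creatinine in range, so a man low in the range can have a large relative rise and cross no limit, while a man near the top can cross one with a small rise. A mean or box plot of absolute change does not supply the missing count.

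The stake is how the endpoint is reported. For the organ of main concern, the frequency tables would show something other than what the endpoint names. For women, the printed grades would hardly separate those who changed from those who did not.

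**Working it through.** The documents state no figure of this kind, so there is none to reproduce. The check applies the printed limits to every admissible baseline.

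**Inputs** (SAP Table 4, mg/dL; Protocol Table 3 prints the same grades)

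| | Reference range | Grade 1 | Grade 2 |
|---|---|---|---|
| Men | 0.76–1.27 | 1.28–1.90 | 1.91–3.80 |
| Women | 0.57–1.00 | 0.58–1.50 | 1.51–3.00 |

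**Grid.** Steps of 0.01 give (1.27 − 0.76)/0.01 + 1 = 52 male baselines and (1.00 − 0.57)/0.01 + 1 = 44 female baselines. Each is multiplied by 1.3, 1.5 or 2.0, rounded to 0.01 and graded.

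**Men**
- *50% rise.* Grade 2 needs a baseline of at least 1.91/1.5 = 1.273, above the reference limit. The one exception is rounding: 1.27 × 1.5 = 1.905, which becomes 1.91. So 51 of 52 stay below Grade 2. Baselines 0.76 to 0.84 are ungraded (0.84 × 1.5 = 1.26), which is 9 of 52. The other 43 of 52 (83%) reach at least Grade 1.
- *30% rise.* None reaches Grade 2 (1.27 × 1.3 = 1.65). Baselines 0.76 to 0.98 are ungraded (0.98 × 1.3 = 1.274, which becomes 1.27), which is 23 of 52 (44%).
- *Doubling.* Every baseline is graded (0.76 × 2 = 1.52). Grade 2 is reached from 0.96 upward, 32 of 52.

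**Women, as printed**
- Baselines 0.58 to 1.00, 43 of 44, already lie in Grade 1.
- *30% or 50% rise.* The highest result is 1.00 × 1.5 = 1.50, still Grade 1. None of the 44 reaches Grade 2, and for those 43 the grade does not move.
- Note 3 to SAP Table 4 reports a TEAE from a baseline overlapping Grade 1 only if the value reaches Grade 2. From those 43 baselines a 50% rise would therefore produce no grade-based laboratory TEAE.
- *Doubling.* Grade 2 is reached from 0.76 upward, 25 of 44.

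**Size of rise needed for Grade 2 from mid-range**
- Men: 1.91/1.015 = 1.88 times baseline. Women: 1.51/0.785 = 1.92 times.
- Both midpoints lie above the CKD-EPI constants 0.9 and 0.7, so the protocol's exponent −1.209 applies. The eGFR falls are 1 − 1.88^(−1.209) = 53% and 1 − 1.92^(−1.209) = 55%.

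**Sensitivity**
- The documents give no baseline distribution. Assume a normal distribution with the male reference range as its central 95%, truncated to that range. A 30% rise is then ungraded for 40% of men and a 50% rise for 7%.
- The eGFR entry limit of 70 can only lower the admissible baseline. At age 45 without the race factor the maximum is 1.23 for men and 0.97 for women. The rounding exception at 1.27 then disappears.

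**The case against.** **Failing to reach Grade 2 is not the same as being missed.** This stands. Most 50% rises in men reach Grade 1, every doubling is graded, and Protocol 9.2.3 enters a new post-dose Grade 1 value as a TEAE.

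**Renal safety does not rest on grades.** This also stands. The change summaries, box plots and biomarkers all use the participant's own baseline, and with 20 participants Listing 9 shows every large rise. It confines the gap to the counts but does not fill it: a reader would have to build the frequency from a listing, and the biomarkers are exploratory.

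**The SAP follows the protocol.** Protocol 11.4.3.2 asks for descriptive statistics of laboratory change, whereas the QTcF categories come from 11.4.6.2. That explains the difference. But both endpoints are frequencies of change, and only the ECG one receives matching counts.

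**The endpoint wording is loose.** The Protocol Summary can be read as a frequency of clinically significant TEAEs. Protocol 3.2.2 and SAP 3.2 are clearer and name changes from baseline as a separate item to be counted.

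**An eGFR value can still become a TEAE.** Protocol 9.2.3 allows this if the investigator finds an ungraded laboratory result clinically significant. That is a judgement on a case, not a tabulated change.

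Three stronger readings are tempting, and the documents do not support them:
- *Zero graded events will be taken as absence of nephrotoxicity.* No section says so, and the study is descriptive, with no hypotheses (Protocol 11.1, SAP 6.8).
- *A 30% rise is often ungraded in women too.* This requires replacing the printed 0.58. If Grade 1 were assumed to start at 1.01, 21 of 44 baselines would be ungraded after a 30% rise and 10 of 44 after a 50% rise. As printed, the number is 0 of 44 for both.
- *The halting rule is faulty because it uses Grade 2.* Protocol 9.5.1 contains no contradiction on this point.

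**Conclusion.** The point holds within limits. The plan states a frequency-of-change endpoint but has no participant count by change in creatinine or eGFR from baseline. The fixed limits are a weak substitute: a 50% rise almost never reaches Grade 2, and a 30% rise leaves 44% of the male in-range values ungraded. The female Grade 1 range conflicts with the reference range and with the rule that creatinine must be in range at entry; those passages must be reconciled.

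These figures are shares of the admissible range, not predicted shares of participants. They assume that the pre-dose Day 1 value is also in range, whereas eligibility is judged at Screening and Day −2. This is a worthwhile, cheap improvement to the reporting, not a failure of renal monitoring.

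**What to change.** Add to SAP 9.6 one table for each safety population, built like the QTcF categories. It should give the number and percentage of participants, with the exact 95% CI already named in SAP 6.1, whose:
- creatinine rises from pre-dose Day 1 by prespecified percentages, for example at least 25%, 50% and 100%;
- eGFR falls by prespecified percentages, for example at least 25% and 50%.

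Show it by timepoint and for the worst value to Day 14, alongside the existing grades. The documents give no such thresholds, so the sponsor should choose them and fix them before data lock; SAP section 15 allows an addendum until then. The interval matters at this size: for 0 of 20 the exact two-sided upper limit is 1 − 0.025^(1/20) = 16.8%.

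Separately, reconcile the female creatinine Grade 1 range in Protocol Table 3 and SAP Table 4 with the reference range and the entry rule.

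The cost is one extra table per safety population from data already collected, with no new samples or visits. The downside is that some fluctuation within the normal range will be counted in the lowest category. No change to the halting rule is proposed.

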#### 9.6.1. Exploratory Biomarkers for Renal Injury

Kidney function biomarkers, serum cystatin C, urinary KIM-1, and KIM-1 normalized per mg urinary creatinine, will be summarized for measurements and change from baseline by parameter and timepoint in Table 49 for the Safety Population and in Table 50 for the Safety Subset Population. Additionally, results will be visualized using box plots showing the change from baseline at each scheduled timepoint for serum cystatin C in Figure 71 and Figure 72, KIM-1 in Figure 73 and Figure 74, and KIM-1 normalized per mg urinary creatinine in Figure 75 and Figure 76 for the Safety Population and Safety Subset Population, respectively.

Results for all kidney function biomarker tests will be listed (Listing 13).

# 9.7. Vital Signs and Physical Evaluations

Toxicity grading criteria for VS results can be found in Table 5. Unscheduled VS measurements will be listed but excluded from tabular and graphical summaries by timepoint, except when calculating the maximum severity post-baseline. VS parameters that have grading criteria for both decreases (results lower than normal range) and increases (result higher than normal range) will be summarized separately by direction of change.

The following VS parameters will be summarized (in order): systolic BP, diastolic BP, HR, respiratory rate, and oral temperature.

VS parameters will be summarized in tables and figures:

- The proportion of participants with mild, moderate, or severe VS results by parameter and timepoint will be summarized (Table 51 for the Safety Population and Table 52 for the Safety Subset Population).
- Summary statistics of measurements and change from baseline by parameter and timepoint will be summarized (Table 53 for the Safety Population and Table 54 for the Safety Subset Population).
- Change from baseline at each scheduled timepoint will be visualized using box plots for each parameter (Beginning at Figure 77 and continuing through Figure 86).

All VS measurements, including height, weight, and BMI, will be presented in Listing 17.

In the case of an abnormal VS measurement, measurements may be repeated up to 2 more times, for a maximum of 3 measurements including the initial measurement at each timepoint. The following rules will be used to decide which measurement to include in the analysis if more than one replicate was entered into the clinical database. VS replicates not used in the analysis will still be included in listings.

- 1. If the first replicate is normal, then it will be used for analysis.
- 2. If the first and second replicates are both abnormal, then the first replicate will be used if it has a severity greater or equal to the second replicate, or the second replicate will be used if the second replicate has a higher severity than the first replicate.
- 3. If the first replicate is abnormal, the second replicate is normal, and the third replicate was not performed, then the first replicate will be used in the analysis.

- 4. If the first replicate is abnormal, the second replicate is normal, and the third replicate is normal, then the second replicate will be used in the analysis.
- 5. If the first replicate is abnormal, the second replicate is normal, and the third replicate is abnormal, then the first replicate will be used if it has a severity greater or equal to the third replicate, or the third replicate will be used if the third replicate has a higher severity than the first replicate.

Abnormal PE findings will be presented in Listing 18.

